8.3.1.1. PK Concentration Data

For analyses based on PK Analysis Sets, PK concentration for all analytes will be summarized by treatment periods.

The following tables will be provided for each analyte (LEN, GS-5423, and GS-2872) using the associated PK Analysis Set by treatment periods:

- Individual participant concentration data and summary statistics

The following figures will be provided for each analyte (LEN, GS-5423, and GS-2872) using the associate PK Analysis Set by treatment periods:

- Mean (\pm SD) concentration data versus time (on linear and semilogarithmic scales). If more than one-third of the values at a timepoint are BLQ then the mean and SD will not be presented at that timepoint and remaining points connected. If lower error bar (mean-SD) is < 0 at a timepoint then it will not be presented at that timepoint.
- Median (Q1, Q3) concentration data versus time (on linear and semilogarithmic scales). If more than one-half of the values at a timepoint are BLQ then the median and quartile values will not be presented at that timepoint and remaining points connected. If lower error bar (Q1) is BLQ at a timepoint then it will be presented as LLOQ at that timepoint.

In addition, the following listings will be provided for all analytes by treatment periods:

- Plasma PK sampling details for LEN by participant, including procedures, differences in scheduled and actual draw times, and sample age.
- Serum PK sampling details for GS-5423 and GS-2872 by participant, including procedures, differences in scheduled and actual draw times, and sample age.

8.3.2. Statistical Analysis of PK Parameters

Individual estimates of pharmacokinetic parameters of LEN, GS-5423, and GS-2872 will be listed and summarized using descriptive statistics by treatment periods (Day 0 to Week 26, and Week 26 to Week 52) (eg, sample size, arithmetic mean, coefficient of variation %, SD, 95% CI for the arithmetic mean, geometric mean, %CV, median, minimum, maximum, Q1, Q3, sample size of natural log-scale [LN], geometric mean, Geometric Coefficient of Variation [%GVC], 95% Confidence Interval for Geometric Mean [GCI], mean of LN, SD of LN).

PK parameters listed in Table 8-1 will be included in the following tables by treatment periods (as applicable).

- Individual estimates and summary statistics of plasma LEN PK parameters using the LEN PK Analysis Set
- Individual estimates and summary statistics of serum GS-5423 PK parameters using the GS-5423 PK Analysis Set
- Individual estimates and summary statistics of serum GS-2872 PK parameters using the GS-2872 PK Analysis Set

PK parameters could be unestimatable due to insufficient concentration data or may be estimated but marked for exclusion due to reasons such as the participant received an incorrect dose. In such cases, the PK parameters will be included in the listing (as not reported [NR] or the estimate values) but will be excluded from the summary statistics, with reasons for exclusion identified.

In addition, determination of half-life and corresponding correlation coefficient will be provided in the following listings by treatment periods:

- Individual data on determination of GS-5423 serum half-life and corresponding correlation coefficient using the GS-5423 PK Analysis Set
- Individual data on determination of GS-2872 serum half-life and corresponding correlation coefficient using the GS-2872 PK Analysis Set

8.4. Changes From Protocol-Specified PK Analyses

There are no deviations from the protocol-specified PK analyses.

9. IMMUNOGENICITY ANALYSIS

Immunogenicity to GS-5423 and GS-2872 will be evaluated based upon the incidence of anti-GS-5423 antibody, anti-GS-2872 antibody, as well as both anti-GS-5423 and anti-GS-2872 antibody formation, respectively.

9.1. Definitions

Participants Evaluable for ADA Prevalence includes all participants who have at least one reportable ADA result at baseline or post-baseline.

Participants Evaluable for ADA Incidence includes all participants who have at least one reportable ADA result at post-baseline.

ADA Prevalence refer to the proportion of participants who have at least one positive ADA sample (baseline or post-baseline) among all participants evaluable for ADA prevalence.

ADA Incidence refer to the proportion of participants who have Treatment-Emergent ADA among all participants evaluable for ADA incidence.

Treatment-Emergent ADA: includes either Treatment-Boosted or Treatment-Induced ADAs, with details been presented in the follows:

- **Treatment-Boosted ADA** is defined as positive baseline ADA sample and at least one positive post-baseline ADA sample and the ratio of the max titer of the post-baseline ADA and the titer of baseline ADA ≥ 4 . If baseline titer < 10 (10 is the minimum reportable titer value), it will be considered boosted if max titer of the post-baseline ≥ 10 . The proportion of participants who have Treatment-Boosted ADA is calculated based on the total number of participants evaluable for ADA incidence as the denominator.
- **Treatment-Induced ADA** is defined as negative or missing baseline ADA sample and at least one positive post-baseline ADA sample. The proportion of participants who have Treatment-Induced ADA is calculated based on the total number of participants evaluable for ADA incidence as the denominator.

Persistent ADA is defined as (a) Treatment-Induced ADA detected at two or more sampling time points during the study, where the first and last ADA-positive sample (irrespective of any negative samples in between) are separated by a period of 16 weeks or longer; or (b) Treatment-Induced ADA detected at the last sampling time point of the study. The proportion of participants who have persistent ADA is based on the total number of participants evaluable for ADA incidence as the denominator.

Transient ADA is defined as Treatment-Induced ADA that does not meet the definition of persistent ADA. The proportion of participants who have transient ADA is based on the total number of participants evaluable for ADA incidence as the denominator.

Neutralizing antibody (NAb) Incidence: the proportion of participants who have treatment-emergent ADA and have at least one positive post-baseline ADA sample detected positive for neutralizing antibody based on the total number of participants evaluable for ADA incidence as the denominator.

Participant-level ADA status is defined as (a) “ADA+” if the participant has Treatment-Emergent ADA; (b) “ADA-” if the participant is evaluable for ADA incidence and does not have Treatment-Emergent ADA; and (c) missing if the participant is not evaluable for ADA incidence.

Participant-level NAb status is defined as (a) “Nab+” if the participant has Treatment-Emergent NAb; (b) “Nab-” if the participant is evaluable for NAb incidence and does not have Treatment-Emergent NAb; and (c) not evaluable if the participant is negative for ADA incidence.

Time to ADA onset is defined as:

- the number of days after first dose to the day when the first positive ADA result was detected for participants with Treatment-Induced ADA
- the number of days after first dose to the day when the first boosted post-baseline positive ADA result was detected for participants with Treatment-Boosted ADA.

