Plasma storage samples for virology testing			X	X	X	X	X	X	X	X	X	X	X		
Immunogenicity (ADA) serum sample ^k								X		X		X	X	X	X
Serum PK samples (GS-5423 & GS-2872) ^{l, m}								X	X	X		X	X	X	X
Plasma PK sample for LEN ^{l, n}								X	X	X		X	X	X	X
Randomization			X												
HIV Treatment Preference Questionnaire			X		X			X				X			
HIVDQoL			X		X			X				X			
HIVTSQs ^o			X		X			X	X			X			
HIVTSQc ^o												X			
Continue baseline oral ART			X												
LEN oral administration ^p								X							
LEN SC administration								X				X			
GS-5423 IV infusion administration ^q								X				X			
GS-2872 IV infusion administration ^q								X				X			

CCI

ADA = antidrug antibody; AE = adverse event; ART = antiretroviral therapy; ARV = antiretroviral; CD4 = clusters of differentiation 4; CD8 = clusters of differentiation 8; DNA = deoxyribonucleic acid; ECG = electrocardiogram; eGFR = estimated glomerular filtration rate; ESDD = early study drug discontinuation; FSH = follicle-stimulating hormone; HBV = hepatitis B virus; HCV = hepatitis C virus; HIV = human immunodeficiency virus; HIV-1 = human immunodeficiency virus type 1; HIVDQoL = HIV-dependent quality of life; HIVTSQc = HIV Treatment Satisfaction Questionnaire change version; HIVTSQs = HIV Treatment Satisfaction Questionnaire status version; IV = intravenous; LEN = lenacapavir; PBMC = peripheral blood mononuclear cell; PK = pharmacokinetic(s); PSD = post study drug; RNA = ribonucleic acid; SC = subcutaneous; TSH = thyroid-stimulating hormone; Wk = week

- a Screening Visit 2 will be performed once results of GS-5423 and GS-2872 sensitivity testing from Visit 1 are reviewed and participant is deemed eligible to proceed.
- b For participants who discontinue the study prior to Week 52, only a ESDD and 30-day follow-up visit is required. For participants who receive study drug in extension phase, refer to Section 6.3.11 for ESDD and post-ESDD 30-, 90-, 180-, 270-, and 365-day follow-up visits. Counsel participant regarding the importance of continuing a complete ARV therapy in accordance with standard of care, and refer participant to an appropriate HIV treatment facility.
- c Vital signs: blood pressure, pulse, and temperature. On dosing days for LEN + GS-5423 + GS-2872, vital signs should be recorded prior to start of study drug administration and 30 minutes (± 10 minutes) after completion of both GS-5423 and GS-2872 infusion, if coadministered or the GS-2872 infusion, if sequentially administered.

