- d Refer to Table 7 for specific tests that are not on a standard chemistry panel (eg, amylase/lipase, uric acid).
- e CD4+ and CD8+ T-cell count at post-ESDD 90-day follow-up visit only.
- f An FSH test is required for participants assigned female at birth who are younger than 54 years, have not undergone permanent sterilization, are not on hormonal contraception, and have stopped menstruating for at least 12 months but do not have documentation of ovarian hormonal failure; see Appendix 11.3.
- g Participants assigned female at birth of childbearing potential only. On Week 52 and subsequent dosing days, urine pregnancy test to be performed predose. During the randomized and extension phase, a positive urine pregnancy test should be confirmed with a serum pregnancy test.
- h HIV-1 genotype and phenotype testing for participants with confirmed virologic failure and HIV-1 RNA ≥ 200 copies/mL. Refer to Section 6.3.9.2.
- i HIV reservoir sample (PBMC) and ECG to be collected at Day 1, Week 26, Week 52, Week 78, and Week 104.
- j CCI [REDACTED]
- k On dosing days, ADA samples must be collected predose.
- l The exact date and time of collection of PK samples must be recorded. PK samples should be drawn from a separate catheter in the opposite arm from the one used for GS-5423 and GS-2872 IV infusions to avoid contamination. Refer to Section 6.3.6 for details.
- m Serum PK samples for GS-5423 and GS-2872 will be collected in all participants as follows:
- Week 52: 0 hours (predose, ≤ 30 minutes prior to dosing of oral LEN) and within 5 minutes after the end of both antibody infusions (GS-5423 and GS-2872), if coadministered or the second antibody infusion (GS-2872), if sequentially administered.
 - Week 78 and Week 104: 0 hours (predose, ≤ 30 minutes prior to dosing of SC LEN).
 - A single any time sample at other scheduled visits.
- n Plasma PK samples for LEN will be collected in all participants as follows:
- Week 52: 0 hours (predose, ≤ 30 minutes prior to dosing of oral LEN) and within 5 minutes after the end of the infusion of both antibodies (GS-5423 and GS-2872), if coadministered or the second antibody infusion (GS-2872), if sequentially administered.
 - Week 78 and Week 104: 0 hours (predose, ≤ 30 minutes prior to dosing of SC LEN).
 - A single any time sample at other scheduled visits.
- o HIVTSQc will only be completed at Week 78. On visits when both HIVTSQs and HIVTSQc will be completed, HIVTSQs should be completed first.

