1.2.2. Extension Phase

At Week 52, participants in Treatment Group 1 who receive the study drug of LEN, GS-5423, GS-2872, and complete the study through Week 52 with HIV-1 RNA < 50 copies/mL at the preceding Week 50 visit will be given the option to participate in the study extension phase. In the study extension phase, participants will continue to receive their randomized study drugs every 26 weeks.

Participants who elect not to participate or are not eligible to participate in the extension phase will resume their baseline oral ART (or appropriate regimen selected by the investigator).

Participants in Treatment Group 3 who complete the study through Week 52 with HIV-1 RNA < 50 copies/mL at the preceding Week 50 visit and in the absence of confirmed VR (as defined in protocol section 6.3.9.2.1) throughout the randomized phase of the study will be given the option to participate in the extension phase and receive the study drugs of LEN, GS-5423, and GS-2872 every 26 weeks at the dose specified for Treatment Group 1. Treatment with LEN, GS-5423, and GS-2872 will start at Week 52 and at that time the baseline oral ART will be discontinued.

Details for study procedures could be found in Section 13 (Appendix 1).

Key Eligibility Criteria

HIV-1 infected participants who meet the following criteria:

- Between 18 and 65 years of age, inclusive, at screening.
- Body weight ≥ 40 kg at Screening Visit 2.
- On stable oral ART consisting of no more than 2 drug classes (with the exception of pharmacologic boosters cobicistat or ritonavir) for ≥ 1 year prior to Screening Visit 2. A change in ART regimen ≥ 28 days prior to Screening Visit 2 for reasons other than virologic failure (VF) (eg, tolerability, simplification, drug-drug interaction profile) is allowed.
- No clinically significant documented historical resistance to the current ART regimen with the exception of isolated nucleoside reverse transcriptase inhibitor mutations including M184V or ≤ 2 thymidine analog mutations (TAMs: M41L, D67N, K70R, L210W, T215Y, and/or K219Q).
- Plasma HIV-1 RNA < 50 copies/mL at Screening Visit 2.
- Documented plasma HIV-1 RNA < 50 copies/mL for ≥ 12 months preceding Screening Visit 2 (or undetectable HIV-1 RNA level according to the local assay being used if the limit of detection is ≥ 50 copies/mL). Virologic elevations of ≥ 50 copies/mL (transient detectable viremia or “blips”) prior to screening are acceptable.

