3. GENERAL CONSIDERATIONS FOR DATA ANALYSES

The Week 52 interim analysis will include all data collected from the randomized and the extension phases of the study. Only data collected in the randomized phase (ie, randomized phase data) will be summarized by treatment group (except that the “by-visit” summary will be up to Week 52 only), if not specified otherwise. Data collected from both phases will be included in data listings. Data included in each phase are defined as follows:

Randomized Phase Data

- For participants who do not enter the extension phase (ie, not treated in the extension phase), all available data are considered as the randomized phase data.
- For participants who enter the extension phase (ie, treated in the extension phase), randomized phase data are defined as data collected **up to** and including the first dose date of the extension phase with the exception as follows: for AEs, concomitant medications, pregnancy, and death, only data collected **prior to** the first dose date of the extension phase are included. For PK/ADA, data collected up to and including the predose timepoint on the first dose date of the extension phase is included.

Extension Phase Data

Extension phase data are only available from participants who enter the extension phase of the study. Extension phase data are defined as data collected **after** the extension phase first dose date with the exception as follows. For AEs, concomitant medications, pregnancy, and death, data collected **on or after** the extension phase first dose date are included. For PK/ADA data, data at postdose on Study Day 1 (EXT) if applicable or after Study Day 1 (EXT) is assigned to the Extension Phase.

In general, analysis results will be presented using descriptive statistics. For categorical variables, the number and percentage of participants in each category will be presented; for continuous variables, the number of participants (n), mean, standard deviation (SD) or standard error (SE), median, first quartile (Q1), third quartile (Q3), minimum, and maximum will be presented.

All statistical tests will be 2-sided and performed at the 5% significance level unless otherwise specified.

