 - last exposure date is defined as the last dose date (randomized phase).

ART Restart Date is defined for treatment group 1 as the earliest ARV start date after permanent discontinuation of LA study regimen for participants who discontinued study drug.

Baseline Value is defined as the following by the treatment group that participants were randomized to:

- Treatment group 1: the last value obtained on or prior to the first dose of the randomized phase.
- Treatment group 3: the last value obtained on or prior to the Study Day 1 (Randomized Phase).

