For Pharmacokinetic and Immunogenicity analyses, the nominal visit as recorded on the CRF will be used when data are summarized by visit. Any data relating to unscheduled visits will not be assigned to a particular visit or time point and in general will not be included in by visit summaries. However, the following exceptions will be made:

- An unscheduled visit prior to the first dosing of study drug may be included in the calculation of the baseline value, if applicable.
- For participants who prematurely discontinue from the study drug or complete the study drug, data collected at early study drug discontinuation (ESDD) visit and post study drug follow-up visits will be summarized in the by visit tables.
- Pharmacokinetic and Immunogenicity data collected at Week 52 pre-dose timepoint for the SBR group will be excluded from the by visit summary tables.

3.8.3. Selection of Data in the Event of Multiple Records in an Analysis Visit Window

Depending on the statistical analysis method, single values may be required for each analysis window up to Week 52. For example, change from baseline by visit usually requires a single value, whereas a time-to-event analysis would not require 1 value per analysis window.

If multiple valid, nonmissing measurements exist in an analysis window, records will be chosen based on the following rules if a single value is needed:

- For baseline, the last nonmissing value on or prior to the first dose date of study drug will be selected, unless specified differently. If there are multiple records with the same time or no time recorded on the same day, the baseline value will be the average of the measurements for continuous data (except for HIV-1 RNA, see below), or the measurement with the lowest severity (eg, normal will be selected over abnormal for safety ECG findings) for categorical data.
 - For postbaseline multiple valid non-missing values in an analysis window, records will be chosen based on the following rules if a single value is needed for an analysis window (Particularly for vital signs, weight and BMI, if postbaseline multiple timepoints exist in an analysis window, single values will be required for each protocol specified timepoint of the analysis window based on the following rules): The record closest to the nominal day for that visit will be selected with the exception of CD4 cell counts and CD4% in which the latest record will be selected and HIV-1 RNA level (see below).

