9.2. Evaluation of Immunogenicity Data

Based on the respective evaluable populations, the following measures of immunogenicity will be reported for (a) ADA prevalence, (b) ADA incidence, (c) Transient/Persistent ADA, and (d) NAb incidence.

The numbers and percentages of participants within each ADA/NAb category described above will be summarized over the entire study period. In addition, the number and percentage of positive ADA and NAb samples will be summarized by nominal visit. ADA titer values in positive ADA samples will be summarized by visit, including median, Q1, Q3, minimum and maximum titer values. Summary statistics for time to ADA onset in ADA+ participants (i.e. participants with Treatment-Emergent ADA) will include median, Q1, Q3, minimum and maximum onset times. Summaries will be provided for each treatment arm and all active treatment groups for the compound of interest combined.

By participant listing of ADA/NAb result, titer, and corresponding PK concentration by participant ID number and visit, as well as participant-level ADA/NAb status, ADA type (persistent or transient), and time to ADA onset will be provided for all participants in the Immunogenicity Analysis Set. A separate listing will be produced for participants with any

positive ADA results. The ADA titer values in ADA+ participants will be plotted over time by individual participant grouped by treatment. For the purpose of plotting, samples with negative ADA result or undetectable titer will have the titer value imputed to zero and connected with the adjacent time points.

In order to evaluate the impact of ADA on PK, combined individual PK concentration-time profile plots by treatment group will be produced with ADA+ participants highlighted in red

The following ADA summary tables will be generated for (1) anti-GS-5423, (2) anti-GS-2872, and (3) both anti-GS-5423 and anti-GS-2872:

- Immunogenicity results over the entire study period, including calculation of ADA prevalence, incidence, and numbers and percentages as well as NAb incidence of participants in each ADA category.
- Numbers and percentages of positive ADA and NAb results by visit
- Median, Q1, Q3, minimum, maximum of titer values in positive ADA samples by visit
- Time to treatment-emergent ADA onset (median, Q1, Q3, minimum, maximum) in ADA+ participants

The following figures will be provided for each analyte, anti-GS-5423 and anti-GS-2872:

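### The SAP's baseline rule makes a positive Week 52 predose ADA sample in Treatment Group 3 count as treatment-induced, although no antibody has yet been given

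*SAP*

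**What the plan says.** **Sampling.** In Protocol Table 2, the Group 3 row "Immunogenicity (ADA) serum sample ^k" has its first mark at Week 52. Screening, Day 1 and Weeks 12, 26, 38 and 50 are empty. SAP Table 13-2 shows the same pattern. The footnote to the row reads: "On dosing days, ADA samples must be collected predose".

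**First exposure.** SAP Section 1.2.2 says of Group 3: "Treatment with LEN, GS-5423, and GS-2872 will start at Week 52 and at that time the baseline oral ART will be discontinued".

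**Baseline.** SAP Section 3.8.1 defines baseline by randomized group. For Group 3 it is "the last value obtained on or prior to the Study Day 1 (Randomized Phase"), and the same section equates that day with the Day 1 visit date. Neither document defines a baseline specific to the extension phase or to the antibodies.

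**Phase assignment.** SAP Section 3, on what belongs to the randomized phase: "For PK/ADA, data collected up to and including the predose timepoint on the first dose date of the extension phase is included".

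**Classification.** SAP Section 9.1 defines treatment-induced ADA as "negative or missing baseline ADA sample and at least one positive post-baseline ADA sample". Treatment-boosted ADA needs a positive baseline sample. Either one makes a case treatment-emergent, and the participant ADA+.

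**Existing safeguard.** SAP Section 3.8.2: "Pharmacokinetic and Immunogenicity data collected at Week 52 pre-dose timepoint for the SBR group will be excluded from the by visit summary tables".

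**Reporting.** SAP Section 9.2 tabulates the participant-level ADA categories over the whole study period, and adds: "Summaries will be provided for each treatment arm and all active treatment groups for the compound of interest combined".

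**The concern.** A label of treatment-induced should mean that the antibody response followed the antibody. For Group 3 the reference point is about a year too early. Day 1 is the start of follow-up on oral ART, and exposure to GS-5423 and GS-2872 begins only at Week 52. The one sample that would serve as a proper pre-exposure baseline is instead read as a response to treatment.

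The incidence of anti-GS-5423 and anti-GS-2872 antibodies is a listed secondary endpoint, and Protocol Section 8.9 has it summarized by treatment group. At stake is whether the Group 3 incidence, status and onset figures describe immunogenicity or merely pre-existing or false-positive assay reactivity.

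**Working it through.** The documents state no figure on this point, so the check is to apply the written rules to one case and then illustrate the size.

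**Step 1: a Group 3 participant positive at Week 52 predose (nominal Study Day 364), then dosed.**

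| Question | Rule | Result |
|---|---|---|
| In the immunogenicity sets? | SAP 3.1.6: randomized, at least one antibody dose, at least one nonmissing result | Yes |
| ADA baseline? | SAP 3.8.1: on or before Day 1; nothing scheduled there | Missing |
| Is Day 364 predose post-baseline? | It falls after Day 1 and is randomized-phase data (SAP 3) | Yes |
| Treatment-induced? | SAP 9.1: missing baseline plus a post-baseline positive | Yes, so ADA+ |
| Antibody given before the sample? | Predose sampling; treatment starts at Week 52 | No |

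With the Week 52 predose sample as baseline, the same participant is baseline-positive and not treatment-induced. A later positive would count only if it met the boosted titer rule.

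**Step 2: consequences within SAP 9.1.**

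- *Boosted ADA.* This needs a positive baseline. Baseline is missing for all of Group 3, so the category cannot occur there, and genuine boosting would be reported as induced.
- *Time to onset.* This is counted from first dose. If that means the first antibody dose, a predose positive falls at about zero, before treatment could have acted. If it means randomized Day 1, onset falls at about Study Day 364. Neither value describes a response to the antibodies.
- *Evaluability.* One post-baseline result is enough. A dosed participant whose only result at the data cut is the predose sample is counted as evaluable for incidence, and as ADA- if it is negative.
- *Persistence.* Part (b) applies if the predose sample is the last one available. Otherwise the case depends on later positives, for which part (a) needs first and last positives at least 16 weeks apart. Positives at Weeks 52 and 64 span 64 − 52 = 12 weeks, too short for part (a). Positives at Weeks 52 and 78 span 78 − 52 = 26 weeks, long enough.
- *Prevalence.* Baseline and post-baseline positives both count, so ADA prevalence does not change.

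**Step 3: which outputs are touched.** The SAP 3.8.2 exclusion covers by-visit tables. The whole-period incidence table, participant-level ADA and neutralizing-antibody status, the onset summary, the plots that pick out ADA+ participants, and the listings of status, type and onset carry no such exclusion.

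**Step 4: size, for illustration.** Let n be the number of Group 3 participants dosed at Week 52 and f the rate of pre-existing or false-positive reactivity per antibody. The planned Group 3 size is 25 (SAP Section 1.3). The documents give no f, so 1% to 5% is assumed.

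P(at least one spurious case) = 1 − (1 − f)^n; expected number = n × f.

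| f | Expected, n = 25 | P, n = 25 | P, n = 20 |
|---|---|---|---|
| 1% | 0.25 | 1 − 0.99^25 = 22% | 18% |
| 2% | 0.50 | 1 − 0.98^25 = 40% | 33% |
| 5% | 1.25 | 1 − 0.95^25 = 72% | 64% |

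As a check on the formula, f = 5% with n = 25 reproduces the 72.3% that SAP Section 1.3 gives for seeing at least one adverse event in Group 3. With 25 in the denominator, each spurious case adds 1/25 = 4 percentage points to Group 3 incidence.

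**The case against.** The best defence is that the text can be read another way. SAP Section 3.8.3 gives a general rule, the last value on or before the first dose date of study drug, and SAP Section 3.1.6 names the antibody in brackets after study drug. A programmer might take Week 52 predose as the ADA baseline without being told to. But the general rule gives way where another is specified, and Section 3.8.1 specifies one for Group 3. Protocol Section 1.2 also counts baseline oral ART as study drug, so even the general rule does not move the Group 3 baseline to Week 52.

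A second defence concerns scope. SAP Section 3 limits by-group summaries to randomized-phase data unless stated otherwise. On that scope the predose sample is ordinarily the only Group 3 result, and whether a group not yet dosed belongs in the sets is itself doubtful. On the whole-period scope of Section 9.2, genuine post-dose samples from Week 64 onward also contribute. The predose sample counts as post-baseline on either scope.

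A third is that the SAP has partly dealt with this sample, and that the listings would let a reader spot a predose positive. That is true, and it limits the harm. It does not correct the tabulated incidence or status.

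Three stronger inferences are not supported:

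- *Every such case is also persistent.* It depends on later samples. The Week 52 analysis waits for all participants to reach Week 52 or discontinue, so earlier entrants may already have later results.
- *Participants never exposed enter the denominators.* The sets in Section 3.1.6 require an antibody dose. The accurate statement is narrower: dosed participants with only a predose result are counted as evaluable.
- *Combined incidence is diluted, say from 5/50 = 10% to 5/75 = 6.7%.* This requires all of Group 3 to be pooled as an active group. Section 9.2 does not settle that, Section 3.2 labels Group 3 as staying on baseline regimen, and the five cases are hypothetical.

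**Conclusion.** Wrong as written, within a limited field. Taken together, the Group 3 sampling schedule, the Group 3 baseline rule and the definition of treatment-induced ADA classify a pre-exposure positive as caused by treatment. The affected outputs are Group 3's overall ADA incidence, participant-level status, time to onset, and the figures and listings built on ADA+ status. Combined summaries are affected only if Group 3 is pooled as an active group.

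Group 1 by-arm results stand, because Group 1 has a Day 1 predose sample (SAP Table 13-1). A reader might infer that the whole immunogenicity endpoint, or efficacy, is compromised; nothing in the documents supports that.

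The classification error needs no numerical assumption. The 22% to 72% chance of at least one spurious case per antibody does: it assumes reactivity of 1% to 5% and that all 25 enter the extension. Entry is optional and conditional on the Week 50 HIV-1 RNA result, so 25 is a ceiling at the planned size. The confirmatory assay tier in Protocol Section 8.9 may keep reactivity low, but the documents do not say how low.

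**What to change.** Amend SAP Sections 3.8.1 and 9.1 for Group 3:

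- define the ADA baseline as the last sample before the first GS-5423/GS-2872 dose, which is the Week 52 predose sample;
- count post-baseline samples, and time to ADA onset, from that dose;
- require at least one post-dose ADA result before a Group 3 participant is evaluable for ADA incidence.

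It would also help to state in Section 9.2 whether Group 3 belongs to the combined active groups.

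The cost is a few sentences and a change to one derivation. No new samples are needed, since the Week 52 predose sample is already scheduled. Group 1 derivations do not change.
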